**Table 3. Anatomic and Radiographic Endpoint Definitions**

Endpoint Definitions			
Endpoint	Response Category	Definition	Point of Measurement
Overall survival	All patients	Death as a result of any cause	Entry onto trial
Event-free survival	All patients	Failure or death as a result of any cause	Entry onto trial
Progression-free survival	All patients	Disease progression or death as a result of PCNSL	Entry onto trial
Disease-free survival	CR, CRu	Time to relapse	First documentation of response
Response duration	CR, CRu, PR	Time to relapse or progression	First documentation of response

*CR requires the following:*

(1) Complete disappearance of all enhancing abnormalities on gadolinium-enhanced MRI.

(2) No evidence of active ocular lymphoma as defined by absence of cells in the vitreous and resolution of any previously documented retinal or optic nerve infiltrates. Chronic changes of the retinal pigment epithelium in the setting of a prior retinal or optic nerve infiltrate does not preclude the definition of a CR. All patients with initial involvement of the eyes on baseline evaluation should have a detailed follow-up evaluation including dilated fundus examination and color photographs of the posterior pole of the eye. Repeat ophthalmologic evaluation is not required for patients without evidence of ocular lymphoma at baseline or interval development of ocular symptoms.

(3) At the time a CR is determined, the patient should have discontinued use of all corticosteroids for at least 2 weeks. Rare exceptions may be made for those patients receiving corticosteroids for another diagnosis (e.g., panhypopituitarism).

*CR/unconfirmed (CRu) includes those patients who fulfill the criteria for CR with the following features/limitations:*

(1) Any patient who fulfills all criteria for CR but continues to require corticosteroid therapy at any dose should be considered an unconfirmed CR. This is critical because corticosteroids may be oncolytic in treating occult tumor. In addition, corticosteroids may decrease gadolinium enhancement on MRI.

(2) Some patients will have a small but persistent enhancing abnormality on MRI related to biopsy or focal hemorrhage. It is often difficult to ascertain whether this represents a residual nidus of tumor or scar tissue. Adjunctive radiologic studies such as single-photon emission computed tomography or positron emission tomography may be helpful, but often the nature of these abnormalities may only be determined by observing the patient with serial scans. If the type of abnormality does not change or slowly involutes over time without therapy and corticosteroids, it is reasonable to categorize it as a CR.

(3) Patients with a persistent minor abnormality on follow-up ophthalmologic examination (persistent non-malignant cells in the vitreous, alteration of the retina/optic nerve that is not consistent with tumor infiltration) may be considered a CRu if this abnormality is unlikely to represent ocular lymphoma.

*Partial response (PR) requires all of the following:*

(1) A  $\geq 50\%$  decrease in the contrast-enhancing lesion seen on MRI as compared with baseline imaging.

(2) Corticosteroid dose is irrelevant to the determination of PR.

(3) Ophthalmologic examination should show a decrease in the vitreous cell count or retinal/optic nerve cellular infiltrate but may continue to show persistent malignant or suspicious cells. Color photos of the posterior pole of the eye should be obtained to document improvement in retinal/optic nerve infiltrates.

(4) No new sites of disease.

Stable disease is defined as less than a PR but is not progressive disease.

*Progressive disease requires the following:*

(1) A more than 25% increase in the contrast-enhancing lesion seen on MRI as compared with baseline or best response (comparison should be made to the smallest of multiple lesions).

(2) Progression of ocular disease as indicated by an increase in the vitreous cell count or progressive retinal or optic nerve infiltration.

(3) Appearance of any new lesion or site of disease (ocular, leptomeningeal or systemic) during or at the end of therapy.

*Relapsed disease (only applicable to patients with a prior CR, CRu) requires the following:*

(1) Appearance of any new lesion.

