#### 3.2 Secondary Endpoints

- 3.2.1** Toxicity will be classified and graded according to the National Cancer Institute's Common Terminology Criteria for Adverse Events (CTCAE, version 5.0).
- 3.2.2** Progression-free survival (PFS) is defined from the date of initiating study treatment to the date of disease progression per the [International Primary CNS Lymphoma Collaborative Group response assessment criteria](#) [37] or death as a result of any cause.
- 3.2.3** Complete Response (CR) is defined using the [International Primary CNS Lymphoma Collaborative Group response assessment criteria](#) for primary CNS lymphoma [37].
- 3.2.4** Duration of response (DoR) is defined as time from documentation of tumor response to disease progression according to the [International Primary CNS Lymphoma Collaborative Group response assessment criteria](#) [37].
- 3.2.5** OS will be measured from the date of initiating study treatment to the date of death or 5 years (whichever is first). Subjects who have not died by the analysis data cut-off date will be censored at their last date of contact.

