### 10.3 Data Analysis Plans

Analysis of efficacy will be conducted following pre-specified inference rule on rejecting the null hypothesis:  $H_0: \text{ORR} \leq 50\%$ . Specifically, we will reject the null hypothesis if and only if there are  $>9$  ORs in the 15 subjects. The main analysis is inferential because we frame it as a hypothesis-testing problem. We will also calculate 2-sided 95% clopper-Pearson confidence interval for ORR.

Secondary endpoints include PFS, CR, DoR, overall survival, and safety/toxicity. Analyses of secondary endpoints will be descriptive. Specifically, time-to-event outcomes like PFS, DoR, and OS will be analyzed using Kaplan-Meier method, and Kaplan-Meier survival curves will be provided. Categorical outcomes like CR, and safety/toxicity (different types of AEs) will be summarized using frequencies.

- For the primary outcome, ORR, there should be no missing data. We will replace non-evaluable cases with new subjects so that the total sample size of 15 evaluable subjects is guaranteed.
- There is only one test for the primary endpoint and hence there is no multiplicity issue.

Per exploratory endpoints:

[REDACTED]

[REDACTED]

[REDACTED]

[REDACTED]

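### PFS is defined in two incompatible ways with no stated precedence, and DoR leaves out death, so Kaplan-Meier DoR would be overstated if responders who die without documented progression are censored

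*Combined protocol and SAP*

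**What the plan says.** Section 3.2.2 opens "Progression-free survival (PFS) is defined from the date of initiating study treatment to the date of disease progression per the" international response criteria, and then adds "or death as a result of any cause". Section 8.4.1 sets out those same criteria. Its Table 3 has a PFS row whose event is "Disease progression or death as a result of PCNSL" and whose point of measurement is "Entry onto trial". Table 3 gives OS that same starting point, whereas Section 3.2.5 starts OS when study treatment is initiated.

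For DoR, Section 3.2.4 reads "Duration of response (DoR) is defined as time from documentation of tumor response to disease progression according to the" same criteria. Table 3 gives the event for response duration as "Time to relapse or progression". Neither mentions death.

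Section 10.3 says that "time-to-event outcomes like PFS, DoR, and OS will be analyzed using Kaplan-Meier method". It does not restate the definitions, name a competing-risk method or give a censoring rule for PFS or DoR. The only time-to-event censoring rule in the visible text is the one for OS in Section 3.2.5. No section says whether 3.2 or Table 3 takes precedence.

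**The concern.** Median PFS and DoR are named secondary objectives (Sections 2.2.2 and 2.2.4), and Section 10.1 says the pilot is to supply preliminary efficacy data before a larger two-arm study. Someone planning that study will read these medians.

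Two things are at stake. First, an analyst who follows the reference in Section 3.2.2 to the response criteria arrives at Table 3, which gives a different PFS event and a different start. If the choice is made after the data are seen, it is open to challenge. The Table 3 event also fits this trial poorly. The trial enrols secondary as well as primary CNS lymphoma, Section 1.4.2 reports fatal treatment-related events with the drug, and no procedure for assigning cause of death is given.

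Second, if death is not a DoR event, the usual handling is to censor a responder at death or at the last scan before it. Kaplan-Meier then treats that subject as still able to progress later. The curve no longer describes the chance of being alive and in response, and it lies above the curve that counts deaths. Death without a documented progression is plausible here. Under footnote 9 of Section 8.1 the scheduled MRIs widen from every 2 cycles to every 3, then every 6, then annually, and are annual for subjects who stop treatment before progression, although symptom-driven scans are allowed.

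**Working it through.** **Texts side by side**

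| Endpoint | Section 3.2 | Table 3, Section 8.4.1 | Agree? |
|---|---|---|---|
| PFS event | progression, or death from any cause | progression, or death from PCNSL | No |
| PFS start | start of study treatment | trial entry (date not defined) | No |
| OS start | start of study treatment | trial entry | No |
| DoR event | progression | relapse or progression | Both omit death |

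**The plan's own figures.** The documents give no assumed median, event count or precision for PFS or DoR, so there is nothing to reproduce for them. The only design figures are for ORR. With 10 or more responders of 15, the exact type 1 error at 50% is 0.1509 (stated 0.15) and the exact power at 70% is 0.7216 (stated 72%). These agree to rounding and do not depend on the PFS or DoR definitions.

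**Effect of leaving deaths out (illustration).** Assumptions that are not in the documents: exponential times, independent causes, and a share s of first events that are uncounted deaths, with s = 10%, 20% or 30%.

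1. Let λ be the hazard of progression or death from any cause. The true curve is exp(−λt), with median ln 2/λ.
2. With the uncounted deaths censored, Kaplan-Meier estimates exp(−(1−s)λt), with median ln 2/((1−s)λ). The median is therefore multiplied by 1/(1−s).
3. This gives 1/0.9 = 1.11, 1/0.8 = 1.25 and 1/0.7 = 1.43.
4. With an assumed true median of 4.5 months, the reported median becomes 5.0, 5.6 or 6.4 months. The 6-month rate becomes 43.5%, 47.7% or 52.4% instead of 39.7%.
5. Over assumed true medians of 3 to 9 months, the 6-month rate is overstated by about 3 points (66.0% against 63.0%, median 9, s = 10%) to 13 points (37.9% against 25.0%, median 3, s = 30%).
6. Simulation check of the 6-month rate, 10,000 Kaplan-Meier curves per setting, true median 4.5 months. At n = 15 the mean is 0.432, 0.480 and 0.523 with deaths censored, against 0.394 to 0.399 with all deaths counted. At n = 10 it is 0.434, 0.476 and 0.522, against 0.395 to 0.396.

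**Per death at this sample size.** If all 15 subjects have a first event, one uncounted death is 1/15 = 6.7%, a factor of 15/14 = 1.07. Two are 13.3%, a factor of 15/13 = 1.15. DoR uses responders only. With 10 responders (the smallest number that meets the success rule), all with a first event, one death gives 10/9 = 1.11 and two give 10/8 = 1.25.

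**Start date.** If entry means the start of the 28-day screening window (an assumption), starting at entry adds at most 28/30.4375 = 0.92 month per subject. If entry means the registration step in Section 11.3, which comes after eligibility is verified and before treatment, the gap may be only days.

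**The case against.** Section 3.0 is the trial's endpoint section and reads naturally as governing. Table 3 sits under a heading that names published criteria, and it lists event-free and disease-free survival, which are not endpoints here. In Section 3.2.2 the reference to those criteria attaches to progression, and the trial adds its own death clause. This stands. Under Section 3.2.2 every death counts, so a reader who infers that PFS will be overstated goes further than the text. That happens only if Table 3 is applied.

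A reader might also infer that toxic deaths would disappear from the efficacy results. They would not. OS counts death from any cause in both places, and a fatal adverse event is an SAE under Section 9.1.5.

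The two DoR definitions both leave out death, so DoR is a gap and not a contradiction. Section 10.3 does not actually say that deaths are censored. Both points are fair, but giving precedence to Section 3.2 does not supply the missing event, and censoring is what an analyst would ordinarily do with the definition as written.

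Finally, PCNSL in Table 3 can be taken to mean the study disease, since Section 8.4.1 applies those criteria to all subjects. That answers part of the literal point on secondary disease, though not the exclusion of toxic deaths. The documents give no split between primary and secondary disease, so no share of affected subjects can be stated.

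**Conclusion.** The PFS definitions conflict in both event and start date, OS conflicts in start date, and no text settles which applies. DoR omits death throughout and, analysed as written, would be biased upward whenever a responder dies without documented progression.

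The size cannot be taken from the documents. The range of 1.11 to 1.43 on the median rests on assumed exponential times and on assumed death shares of 10% to 30%. It would be wrong to read it as what one or two deaths do to PFS: among 15 first events they give about 1.07 to 1.15, and 1.43 would need four to five. Each death weighs more in DoR because the denominator is smaller. The start-date effect is at most about 0.92 month and probably less.

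The consequence is moderate. The ORR test is untouched and the secondary analyses are descriptive. The change is still worth making, because these medians are named objectives and the repair is simple.

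**What to change.** - **PFS and OS.** State, in Section 8.4.1 or 10.3, that Section 3.2 governs for this trial: both start at first dose, and the PFS event is progression or death from any cause. Mark the endpoint rows of Table 3 as reference text, or align them with Section 3.2.
- **DoR.** In Section 3.2.4, define it as the time from first documented CR, CRu or PR to progression, relapse or death from any cause, whichever comes first. Censor subjects with none of these at their last disease assessment. PFS also lacks a censoring rule, and the same sentence could serve it.

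The cost is wording only, with no new data, visits or subjects. The reported medians may be slightly less favourable.

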### 1.2 Disease Background

PCNSL is an uncommon variant of extranodal non-Hodgkin lymphoma (NHL) that involves the brain, leptomeninges, eyes, or spinal cord without evidence of systemic disease. PCNSL represents approximately 4% of newly diagnosed primary CNS tumors [3, 4]. Secondary involvement of the CNS from systemic NHL may affect the nervous system at every level, including peripheral nerve, spinal nerve root, spinal cord, meninges, and brain. Such involvement may include direct invasion or compression of these structures, as well as non-invasive paraneoplastic effects of NHL. Both relapsed primary (PCNSL) and secondary CNS lymphomas (SCNSL) have a dismal prognosis, with untreated patients living for only several months [5]. Most data evaluating relapsed PCNSL are retrospective in nature, but traditional options are limited in this situation and include radiation, temozolomide, etoposide and cytarabine, all with modest response rates and poor long-term survival [5]. Furthermore, many of these patients are heavily pretreated and may have difficulty tolerating very aggressive cytotoxic chemotherapy regimens. In a study of aggressive chemotherapy in patients with SCNSL, the CR rate was only 22% with a one-year overall survival (OS) of 25% demonstrating the need for novel approaches other than traditional cytotoxic agents [6]. Therefore, more effective and well tolerated regimens are desperately needed.

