## 4.2 Exclusion Criteria

Subjects meeting any of the following exclusion criteria will *not* be able to participate in this study

- 4.2.1** Prior cancer treatment that was completed less than 14 days prior to Day 1 of study dosing or if subject has not recovered from all reversible acute toxic effects of the regimen to grade  $\leq 1$  or baseline.
- 4.2.2** Prior brain radiotherapy under the following conditions:
- Whole-brain radiotherapy (WBRT) that was completed less than 28 days prior to Day 1 of study dosing
  - Stereotactic radiosurgery (SRS) that was completed less than 14 days prior to Day 1 of study dosing.
- 4.2.3** Currently receiving or has received an investigational agent within 28 days of first dosing with study treatment. Subjects should not currently be receiving investigational treatment or have received an investigational agent within 28 days of dosing.
- 4.2.4** Subject is pregnant or breastfeeding (*Note*: breast milk cannot be stored for future use while the mother is being treated on study).
- 4.2.5** Subject has active CSF involvement that requires ongoing intrathecal chemotherapy.
- 4.2.6** Previous exposure to a BTK inhibitor.
- 4.2.7** Subjects with severe hepatic insufficiency, as defined by [Child-Pugh Score](#)  $> 6$  ([Appendix C](#)).
- 4.2.8** Subject is receiving prohibited medications or treatments as listed in [Section 5.3](#) of the protocol that cannot be discontinued/replaced by an alternative therapy. Subject requires treatment with a strong cytochrome P450 3A4 (CYP3A4) inhibitor/inducer (please consult [Section 5.3](#)). Subjects may be eligible if they are medically able to discontinue CYP3A4 inhibitors/inducers at least 14 days before the first dose of study treatment.
- 4.2.9** Subject requires or receiving anticoagulation with warfarin or equivalent vitamin K antagonists (e.g., phenprocoumon) within 14 days of first dose of study drug. Subjects requires or is taking direct oral anticoagulants (e.g. apixaban, rivaroxaban, edoxaban, lovenox) within 7 days of first dose of study drug.
- 4.2.10** Subjects receiving capsule form of acalabrutinib may not be taking proton pump inhibitors (e.g., omeprazole, esomeprazole, lansoprazole, dextansoprazole, rabeprazole, or pantoprazole). Subjects receiving proton pump inhibitors who

switch to H2-receptor antagonists or antacids and subjects receiving tablet form of acalabrutinib are eligible for enrollment to this study.

[figure not shown]

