#### **7.4.2 Cerebrospinal Fluid Uptake of Acalabrutinib**

Cerebrospinal fluid sample (3 – 4 mL) will be collected when possible after (2 +/- 1 hours) oral administration of acalabrutinib to characterize its uptake. Residual sample, if available, will be stored and may be used for future research related to the study.

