9. MRI of brain should be obtained at screening within 28 days prior to start of study treatment and while on treatment at C3D1 ( $\pm 7$  days), C5D1 ( $\pm 7$  days), C7D1 ( $\pm 7$  days), C10D1 ( $\pm 7$  days), C13D1 ( $\pm 7$  days), C19D1 ( $\pm 7$  days), C25D1 ( $\pm 7$  days), and then annually ( $\pm 30$  days) for up to five years, or as needed, if there are any clinical signs/symptoms of progression. Scans will be continued until disease progression. If a subject comes off treatment for any reason other than disease progression (e.g. adverse events or withdraw from treatment), then the subject will have an MRI of the brain annually ( $\pm 30$  days) for up to 2 years or until disease progression.
10. Rubidium PET-CT performed at screening, C3D1 ( $\pm 7$  days), and C7D1 ( $\pm 7$  days), in the first 5 subjects at the University of North Carolina who consent to the procedure.
11. CT or PET-CT imaging will be performed at screening in order to confirm no evidence of systemic involvement of lymphoma. A prior scan showing no evidence of systemic involvement can be utilized, as long as it is performed within 28 days of starting study drug.
12. Ocular exams will be performed during screening only if the subject has ocular symptoms or recommended per standard of care. Subjects with active ocular lymphoma will have ophthalmologic evaluation (exam or imaging) to confirm CR.

13. Cerebrospinal fluid sample (3 – 4 mL) will be collected at 2 hours (+/- 1 hour) after oral administration of acalabrutinib at Cycle 1 Day 1 and Cycle 1 Day 8. Subjects who cannot have CSF samples drawn may remain in the study.
14. Acalabrutinib treatment will continue until the subject shows signs of disease progression, unacceptable toxicity, or withdraws from the study.
15. Toxicity assessment per NCI-CTCAE criteria, v.5.0.
16. Blood samples for pharmacokinetic analysis will be collected prior to acalabrutinib dosing and at 1, 2, and 4 hours after oral administration of acalabrutinib on Day 8 of Cycle 1. It is important to collect the time of last dose at each time point.
17. Testing of tumor sample for MYD88 and CXCR4 will be collected at baseline (Cycle 1 Day 1 prior to treatment initiation). Testing will only be carried out if there is sufficient tissue available. This may be from an archival sample or a fresh biopsy collection if collected per standard of care.

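### Section 8.4.1 has no condition for CSF or spinal disease known at baseline, so such a subject can be recorded as CR when the brain MRI clears; the firm effect is on the secondary CR rate, not on ORR

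*Combined protocol and SAP*

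**What the plan says.** **Who can enter.** Section 1.2 describes primary CNS lymphoma as a disease that "involves the brain, leptomeninges, eyes, or spinal cord without evidence of systemic disease", and says that secondary involvement can reach the spinal cord, nerve roots and meninges. Exclusion 4.2.5 reads "Subject has active CSF involvement that requires ongoing intrathecal chemotherapy". No other criterion mentions CSF, leptomeningeal or spinal disease. Inclusion 4.1.5 requires parenchymal disease only of subjects with intra-ocular lymphoma.

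**How response is judged (Section 8.4.1).**
- CR has three items: "Complete disappearance of all enhancing abnormalities on gadolinium-enhanced MRI"; an eye item beginning "No evidence of active ocular lymphoma as defined by absence of cells in the vitreous"; and corticosteroids stopped for at least two weeks.
- PR asks for at least a 50% decrease of the enhancing lesion on MRI, improvement on eye examination, and "No new sites of disease". Steroid dose is irrelevant.
- The PD item that names the leptomeninges reads "Appearance of any new lesion or site of disease (ocular, leptomeningeal or systemic) during or at the end of therapy".

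**What is scheduled.** Footnote 9 to the Time and Events Table begins "MRI of brain should be obtained at screening within 28 days prior to start of study treatment", and the on-treatment scans it lists are of the brain too. No spine MRI or CSF cytology is scheduled at any visit. CSF is drawn at Cycle 1 Days 1 and 8 to measure drug uptake, and subjects who cannot be sampled stay in the study (footnote 13). Of leftover CSF, Section 7.4.2 says only "Residual sample, if available, will be stored and may be used for future research related to the study".

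**The concern.** The plan treats the eye and the other non-brain compartments differently. For the eye, footnote 12 and CR item 2 require an examination of disease present at baseline before CR can be called. For CSF, leptomeninges and spine there is no matching condition. Those sites enter the written rules by name only in the PD definition, and only as something new.

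Two gaps follow. First, persistence of known CSF lymphoma, or of a known spinal deposit that is not re-imaged, does not prevent CR. Second, worsening of a known CSF site that does not enhance on the brain MRI meets no PD item and breaches no PR item, because the site is not new.

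The CR rate is a secondary endpoint (Section 3.2.3), and the synopsis calls any complete response clinically notable. With 15 evaluable subjects, one wrong CR is visible in the reported rate.

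**Working it through.** **1. The rules side by side**

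| Compartment involved at baseline | Blocks CR if it persists? | Counts as PD if it worsens? | Scheduled test on treatment? |
|---|---|---|---|
| Brain | Yes, CR item 1 | Yes, PD item 1 | Brain MRI |
| Eye | Yes, CR item 2 | Yes, PD item 2 | Eye evaluation to confirm CR |
| Spine, or leptomeninges enhancing on MRI | Yes if imaged; item 1 does not say brain | Yes if imaged; PD item 1 does not say brain | None for spine; brain MRI may show some leptomeningeal enhancement |
| CSF, non-enhancing | No | No; item 3 covers new sites only | None |

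The gap is the last row, plus spinal disease that nobody re-images.

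**2. The plan's own figure.** Inputs from Sections 10.1 to 10.3: n = 15, reject at 10 or more responders, null ORR 50%, alternative 70%. The probability of rejection is the sum over k = 10 to 15 of C(15,k) p^k (1−p)^(15−k).
- At p = 0.50: (3003 + 1365 + 455 + 105 + 15 + 1)/32768 = 4944/32768 = 0.1509. The plan states 0.15.
- At p = 0.70: 0.7216. The plan states 72%.

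Both agree to two decimals. The point here does not depend on them.

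**3. Effect on the CR rate.** One subject is 1/15 = 6.7 points. The ibrutinib CR rates quoted in Section 1.1 correspond to 0.17 × 15 = 2.6 and 0.45 × 15 = 6.8 subjects, so one false CR is material against that yardstick.

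**4. Effect on ORR.** Section 3.1 defines ORR as PR + CR.
- Brain lesion clears and known CSF disease persists: recorded as CR, and PR under the fix. The subject is a responder either way, so the change in ORR is 0.
- Brain lesion shrinks and known CSF or spinal disease worsens: recorded as PR or CR, and a non-responder if worsening counts. The change in ORR is 6.7 points per subject.

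Only the second case reaches the decision rule. One such subject can turn 9/15 (60.0%, not rejected) into 10/15 (66.7%, rejected). As an illustration, assume that m of the 15 are always recorded as responders and the rest respond at 50%. The chance of rejection is then P(X ≥ 10 − m) with X binomial(15 − m, 0.5):
- m = 0: 0.151
- m = 1: 3473/16384 = 0.212
- m = 2: 2380/8192 = 0.291

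Nothing in the documents says that m is above zero.

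**5. How many subjects?** The documents give no prevalence. If 10% to 30% of subjects had CSF or spinal disease (assumption), that would be 1.5 to 4.5 of 15. A false CR also needs the brain to clear. Applying the quoted 17% to 45%, and assuming independence, gives 0.17 × 1.5 = 0.3 to 0.45 × 4.5 = 2.0. That is before requiring that the other site persists and goes undetected, so the expected number of false CRs under these assumptions is lower still.

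**The case against.** **A reader might infer that the primary endpoint is inflated.** The documents do not support this for persisting disease. PR tolerates residual lymphoma by design; in the eye, malignant cells may remain. Persisting CSF disease beside a brain PR is therefore not in itself a misclassification, and moving a subject from CR to PR leaves ORR unchanged. The go-forward decision rests on ORR (Sections 1.1 and 10.3), while CR is summarised descriptively.

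**A reader might also infer that any spinal or leptomeningeal deposit is ignored.** That goes too far. CR item 1 and PD item 1 refer to MRI without limiting it to the brain, so enhancing disease seen on any MRI already counts. New leptomeningeal sites are PD. Footnote 9 allows extra MRI for symptoms, although of the brain. What remains is CSF disease without enhancement, and spinal disease that is not imaged.

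**The criteria are taken from a published source**, reference 37. Whether that source has a CSF item cannot be checked from the documents. The rules written out in Section 8.4.1, which sites would apply, have none. If the source has one, the gap is an incomplete transcription and the same wording closes it.

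**Eligibility is by silence.** No criterion expressly admits CSF or spinal disease, so possibly no such subject enrols. That limits the size of the problem, but the rule would still be wrong for any subject who does.

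**Conclusion.** The point holds in a narrow form. As written, Section 8.4.1 allows CR in a subject whose CSF lymphoma, or un-reimaged spinal lymphoma, was known at baseline and has not been shown to clear. It also does not register worsening of a known, non-enhancing CSF site.

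The firm consequence is possible overstatement of the secondary CR rate, by 6.7 points per affected subject. ORR, PFS and DoR are exposed only where known CSF or spinal disease worsens while the brain lesion shrinks. The number affected cannot be derived from the documents; a count based on everyone with CSF or spinal disease would overstate it, because most of them need not be false CRs.

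The conclusion rests on two readings: that silence in Sections 4.1 and 4.2 leaves such patients eligible, and that sites apply Section 8.4.1 as printed.

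**What to change.** Change the wording of Section 8.4.1 and add one eCRF field:

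1. Record the CNS compartments known from existing clinical results to be involved at baseline: brain, eye, CSF/leptomeninges, spine. Allow unknown as an entry.
2. CR requires documented clearance of every compartment recorded as involved. If such a site is not re-examined, the best category is PR.
3. Documented worsening of a known CSF, leptomeningeal or spinal site counts as PD and precludes PR. The sponsor should state what counts as documented worsening.
4. Report the number of CRs in subjects whose CSF status is unknown.

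Keep brain MRI in footnote 9. Replacing it with imaging of the sites involved at baseline would be circular at screening and would drop brain MRI for subjects without known brain disease. Mandate no new lumbar puncture or spine MRI. The study CSF samples cannot supply baseline status reliably: they are optional, and the first is taken about two hours after dosing.

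**Cost.** Because no CSF is scheduled after Cycle 1 Day 8, CSF-positive subjects who are not re-tested clinically cannot be CR. The CR rate may be slightly lower, which errs on the conservative side; the cap leaves ORR unchanged. Item 3 concerns classification for analysis. Since Section 5.4 lists progression as a point at which treatment ends, the sponsor should state how the two passages relate.
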